1936 At the first meeting the DSMB will discuss the protocol, suggest modifications, and establish 1937 guidelines to study monitoring by the Board. The DSMB Chairperson in consultation with the 1938 Principal Investigator and the NIA Program Official will prepare the agenda to address the 1939 review of study materials, modifications to the study protocol and informed consent document, 1940 initiation of the trial, appointment of a safety officer, as needed, reporting of adverse events, 1941 statistical analysis plan including interim analysis and stopping rules, etc. 1942 1943 Meetings of the DSMB will be held 2-4 times per year at the call of the Chairperson and / or NIA 1944 Program Official to ensure patient safety and to review stopping rules for the trial. The NIA 1945 Program Official or designee will attend most of the meetings. An emergency meeting of the 1946 DSMB may be called at any time by the Chair or by the NIA should participant safety questions

- 1947 or other unanticipated problems arise.
- 1948

1949 Meetings are closed to the public because discussions may address confidential participant

1950 data. Meetings are attended by the Principal Investigator and members of his/her staff.

1951 Meetings may be convened as conference calls as well as in-person.

1952

1953 Meeting Format

Each meeting must include a recommendation to continue or to terminate the study and
whether the DSMB has any concerns about participant safety made by a formal DSMB majority
or unanimous vote. Should the DSMB decide to issue a termination recommendation, the full
vote of the DSMB is required. In the event of a split vote, majority vote will rule and a minority
report should be appended. The DSMB Chair provides the tiebreaking vote in the event of a 5050 split vote.

1960

A recommendation to terminate the study may be made by the DSMB at any time by majority vote. The Chair should provide such a recommendation to the NIA immediately by telephone and email. After the NIA Director makes a decision about whether to accept or decline the DSMB recommendation to terminate the study, the PI is immediately informed about his decision.

1966

1967 Meeting Materials

DSMB interim report templates will be prepared by the study staff, to be reviewed by the DSMB
members at each meeting. The reports will list the study aims, the status of the study, and
summarize safety data.

1971

1972 **Reports from the DSMB**

1973 A formal report containing the recommendations for continuation or modifications of the study

1974 will be prepared by the DSMB Chairperson, NIA Program Official or its designee. The draft

1975 report will be sent to the DSMB members for review and approval.

1976

1977 **Confidentiality**

1978 All materials, discussions and proceedings of the DSMB are completely confidential. Members

and other participants in DSMB meetings are expected to maintain confidentiality.

1981	PATIENT-CLINICAN STAKEHOLDER ADVISORY COMMITTEE ROLE
1982	This study is guided by a Patient-Clinical Stakeholder Advisory Board that is comprised of
1983	patients and patient advocates (including native Spanish-speakers), surrogates, and
1984	ZSFG/SFHN primary care clinic staff and medical directors. These individuals are paid key
1985	personnel on the study and have agreed to meet up to 4 times per year to oversee all aspects of
1986	the study. Native Spanish-speaking staff will be present to translate for our Spanish-speaking
1987	patient stakeholders during advisory meetings. All study materials will be translated into
1988	Spanish. The advisory committee will be involved in providing ongoing advice about the
1989	following important study related activities:
1990	Recruitment, including study scripts, fliers, methods
1991	Eligibility and exclusion
1992	Patient safety and research staff safety
1993	Clinic workflow and clinical champions
1994	Informed consent
1995	Research outcomes
1996	Presentation of findings
1997	Dissemination of results
1998	

Summary of Changes to the Protocol: The listed topics follow the outline and headers of the protocol

Торіс	Date	Summary of Changes
Funding	Feb 3, 2014	We obtained funding from the National Institute on Aging (R01AG045043) to start recruitment of English-speakers. We then also obtained Patient-Centered Outcomes Research Institute (PCORI) funding (R-1306-01500) to add Spanish-speakers to our established trial infrastructure and protocol.
Funding	Mar 8, 2017	[name] became funded, in part, by a NIA K24 (K24AG054415).
ClinicalTrials.gov registration	Feb 27, 2014	When PCORI funding was obtained, PCORI required a separate Clinical.Trial.gov number. Thus, it was added in February 2014. Although English- and Spanish-speaking recruitment was supported by two funders, this was one trial with the same staff, locations, procedures, IRB, and protocol. ³⁶
Background	Apr, 2016	We updated the background to included updated references.
Preliminary Studies	May, 2017	We updated the preliminary studies to include the findings from our published VA trial. The name of hospital was changed on May 3 rd , 2015 from SFGH to Zuckerberg San Francisco General Hospital (ZSFG). This change was made throughout the protocol.
Overview of Trial	Jan 4, 2016	We updated the protocol to include our study flow diagram for our records.
Eligibility screening	Jan 16, 2014	Eligibility screening in busy, loud, outpatient clinics was often difficult. With our patient- clinicians stakeholders, we decided to include the ability to recruit and screen by phone. See below under recruitment.
Exclusion criteria	Jul 15, 2014	To minimize potential contamination, we excluded participants who may have been exposed to the PREPARE website from other sources such as being in a PREPARE- related focus group or pilot study.
Exclusion criteria	Oct 3, 2014	To ensure the safety of our research staff, we excluded potential participants with evidence of active drug or alcohol abuse within the past 3 months determined by clinician assessment, self-report, chart review or research staff assessment.
Exclusion criteria	Jan 16, 2014	To minimize the risk of unblinding by fellow research participants, any spouse/partner of a currently enrolled patient or an individual who is named as an enrolled patient's potential surrogate decision maker (regardless of cohabitation or spousal status), who is also a patient at SFHN/ZFG will be excluded from being a patient participant. This will avoid a situation where 2 closely related people living in the same home could be randomized to different study arms and result in unblinding.

Exclusion criteria	Jan 27, 2014	To save research staff considerable time and effort, potential participants who initially scheduled but then missed the baseline interview (i.e. no show) more than 2 times without prior notification and rescheduling with study staff will be considered ineligible, unless there were significant extenuating circumstances.
Spanish Translation	Nov 13, 2014	All translated and back-translated study materials were approved by the UCSF IRB.
Recruitment methods	Nov 13, 2013	We initially sent opt-out letters to potential participants. However, many SFHN/ZSFG patients are marginally housed, had incorrect mailing addresses, or have limited literacy. We also discovered that many patients were confusing the opt-out letters for bills from the hospital. With input from our Patient-Advisory Board and DSMB, we switched to more engaging recruitment letters and postcards that allowed patients to call and hear more about the study or to opt-out. They could also opt-out at any time.
Recruitment methods	Jan 16, 2014	It was determined by our patient-clinician stakeholders that it would be acceptable to recruit patients by phone in addition to in clinic recruitment. In addition, because we were attempting to enroll patients 1-3 weeks prior to a primary care visit, it was proving difficult to approach patients in clinic ahead of their primary care appointments. In addition, our primary care stakeholders felt it would be better for their clinic workflow to not have research staff always in the clinic. Therefore, we expanded our recruitment options, after receiving permission from the clinician and sending recruitment letters, to both approach potential participants in clinic as well as recruit by phone.
Recruitment- reimbursement	Jan 16, 2014	We initially reimbursed \$25 separately for the screening interview and \$25 for the baseline interview that included intervention exposure. We realized that the screening interview was brief and often occurred over the phone because it was difficult to conduct in busy clinic settings. We also realized, in collaboration with our patient-clinician advisory board, that it made more sense to reimburse participants for \$50 for the baseline interview since these interviews were longer and in our study offices. We also changed from taxi vouchers to municipal transportation tokens because of the increased surcharge associated with taxi vouchers and participant preference.
Consent forms	Jan 27, 2014	For staff safety and the need to exclude or withdraw participants who were intoxicated, psychotic, or threatening, the consent also explains, "We also may ask you to stop taking part in this study if we feel it is in your best interest or if you do not follow the study rules."
Consent forms	Jan 27, 2014	Clinicians needed to be contacted if their patient reported severe depression or anxiety. We updated our consent forms to fully explain this to participants:

		"We would need to contact your regular doctor or a medical provider for the following reasons: -You report or we observe that you are having:
		A medical emergency such as a serious medical illness
		Or, a serious mental illness, such as major depression
		 You report that you may harm yourself, you may harm someone else, or someone is harming you
Randomization	Jan 16, 2014	The initial IRB application was a Just-in-time submission for an NIH proposal. We initially planned to block randomize, as we did for a recent VA trial, ³⁵ by both health literacy and race/ethnicity. However, given the diversity of patients at SFHN/ZSFG (over 50% non-white), in comparison to the VA, we decided to only block randomize by health literacy.
Data Collection Methods	Jan 16, 2014	To be more environmentally-conscious, we switched from paper surveys to use the LiveCapture function of RedCap. We retained the use of paper surveys in the event the RedCap system was down. All paper files continued to be stored in secure, locked research offices in secure, locked file cabinets.
Follow-up & Retention	May 28, 2014	We created an appointment reminder sheet to show the dates and times for upcoming primary care appointments as well as upcoming study appointments to help with retention.
Follow-up & Retention	Jan 16, 2014	We expanded the options for follow-up interviews to be not only in the clinic or by phone, but also in the home if needed as many of our patients had functional limitations.
Follow-up & Retention	Jul 15, 2014	For all participants who missed their primary care appointment and did not reschedule, we provided a courtesy phone call to remind participants to reschedule the primary care appointment.
Follow-up & Retention	Jul 15, 2014	Patients were enrolled based on upcoming primary care appointments. All follow-up interviews were timed to this primary care appointment. Some primary care appointments were subsequently missed or cancelled. In consultation with our stakeholder advisory committee and the DSMB, we decided that for participants who reschedule and attend their primary care appointment within 6 months, we would still conduct interviews at 1 week, and at 3, 6, and 12 months from the primary care appointment date. If participants do not reschedule within 6 months, we will conduct follow up assessments at 6 and 12 months from the primary care appointment date.

Follow-up and Retention	Jan 16, 2014	All data capture was by verbal survey administration and many of our follow-up interviews occurred over the phone. To help participants follow along during the interview, we mailed out a Participant Version of the survey to be used during the phone call if desired. No data were collected by mail.
Measures & Data Collection	Jan 4, 2016	We created a table displaying all study oucome measures, including validity and reliability information in both English and Spanish, number of survey items, references and the schedule of administration for our records and protocol.
Measures & Data Collection	Mar 12, 2013	Correction: A priori , we planned to collect ACP documentation data at 15-months (not 12 months as stated in our original and published protocol) to mirror the methods used in our previously published trial of PREPARE in the VA setting. ³⁵ We fixed this typo in our final protocol. From the prior VA trial, ³⁵ it was estimated that the time from the intervention to the primary care visit and the average time to schedule and conduct the final patient interview would be 3 months. Therefore, we standardized this window for all participants in this and our prior published trial. ³⁵
Measures & Data Collection	Jan 16, 2014	We initially proposed to screen for depression and anxiety using the -Patient Health Questionnaire-2 item (PHQ-2) and the Generalized Anxiety Disorder-2 item (GAD-2). Our DSMB felt more precise versions of this survey should be used. Therefore, we updated our methods to reflect assessment of depression and anxiety using the Patient Health Questionnaire-8 item (PHQ-8) and Generalized Anxiety Disorder-7 item (GAD-7).
Measures & Data Collection	Sept 20, 2017	Our Patient-Advisory Stakeholders requested we quantify the number and percentage of patients who increased their ACP activities overtime. Our stakeholders perceive any increase in an ACP activity over time as clinically meaningful. Thus, in addition to mean change in ACP Engagement scores, they wanted to know the percent of patients who improved over time for Behavior Change scores, Actions scores, and both combined. We defined improvement as an estimated overall slope > 0. Therefore, we created this exploratory variable post-hoc and used Bonferroni corrections to set the p-value of significance at 0.017.
Human Subjects Protections	May 28, 2014	Because we were assessing depression and anxiety as part of the trial, to err on the side of caution, the Patient-Clinician Stakeholder Advisory Board helped us create a flow diagram with detailed instructions, scripts, and telephone numbers for how staff could refer participants who report severe depression/anxiety if that were to occur. As above, this potential disclosure of participant information was provided on the informed consent form.

2001 Summary of Changes to the Statistical Analysis Plan

Торіс	Date	Summary of Changes
Refusals & withdrawal comparisons	Sep 30, 2016	We added a description of our planned analysis to compare participants who refused based on age and self-reported gender. We also added a description of our planned analysis to compare reasons for withdrawal between study arms.
Bonferroni corrections	Sep 30, 2017	We added Bonferroni adjusted p-values for all secondary and exploratory outcomes.
Stratifying results by language	Mar 1, 2014	Our PCORI grant was funded on Mar 1 st , 2014 and allowed us to add Spanish- speaking participants to the trial. A priori and based on prior literature and the preferences of our stakeholders and grant funders, we added information about stratifying our analysis based on English and Spanish-speaking participants.
Models	Sep 30, 2016	We explain more fully the modeling terms in the mixed effects models.
Variable added to adjusted models	Sep 30, 2016	In addition to health literacy and clustering by clinician, we also adjusted all mixed effects models for baseline ACP documentation because, in consultation with our stakeholders, it was felt that these patients may be different from ACP naïve participants. This also mirrors the analysis in the prior VA PREPARE trial. ³⁵
Effect Size Definitions	Sep 30, 2016	We added information and references concerning clinically meaningful effect sizes.
Exploratory Outcome	Sep 30, 2016	Based on stakeholder request, we included a description of an added exploratory outcome to calculate the percentage of participants who increased their ACP Engagement scores. Bonferroni adjusted p-values for this post-hoc analysis were adjusted to a significance level of 0.017.
Interactions	Sep 30, 2016	We more clearly defined the variables used to test for interactions and how these variables were dichotomized for analysis.

2003 FINAL PROTOCOL REFERENCES

- The United Nations Department of Economic and Social Affairs Population Division.

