1649 Our primary analyses will compare change in ACP documentation between study arms from 1650 baseline to 15 months. Secondary outcomes will include ACP Engagement with respect to 5 1651 ACP Actions (yes/no and a 0-25-point scale) and behavior change scores (average 5-point 1652 Likert scores) from baseline to 1 week, and 3, 6, and 12 months. Variables will be assessed for distributional and outlier values using standard summary statistics. Baseline comparability will 1653 1654 be assessed between groups using unpaired t-tests, Chi-square tests or Fisher's exact tests. 1655 Using t-tests or Chi-squared tests, we will also compare patient's age and self-reported gender 1656 between those who refused versus those who enrolled and differences between arms of those 1657 who withdrew versus those who did not. We will use intention-to-treat analysis using SAS 1658 version 9.4 (SAS Institute Inc.) and STATA 15.0 (College Station, TX). All p-values will be 2-1659 tailed and set at .05 for the primary outcome and Bonferroni adjusted for secondary patient-1660 reported outcomes. In addition, because of differences in ACP engagement among English and Spanish speakers,⁸ and based on preferences of our stakeholders and granting agencies, we 1661 1662 decided, a priori, to analyze our results overall and stratified by English and Spanish language. 1663 To compare outcomes between the two arms longitudinally, we will use mixed effects linear, 1664 Poisson, or negative binomial regression for continuous measures and mixed effects logistic regression for dichotomous measures. The mixed effects models will include fixed effects for the 1665 1666 primary modeling terms of time (baseline and 15 months for ACP documentation and baseline 1667 and 1 week, 3 months, 6 months, and 12 months for ACP Engagement with time modeled using 1668 dummy variables to allow for non-linearity); arm (AD-only versus PREPARE); an interaction 1669 term of study arm and time; and a random effect for subjects. We will adjust for the randomization blocking factors limited vs. adequate literacy,⁹⁸ and any predictor variables that 1670 1671 differ between arms. All models also will also be adjusted for baseline ACP documentation and will include random physician intercepts to account for nesting of patients within physicians. We 1672 1673 will use standardized, clinically meaningful effect sizes (i.e., 0.20-0.49 small, 0.50-0.79 medium,

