and ≥ 0.80 large).⁹⁹ Per stakeholder request, we will conduct post-hoc mixed-effects regression to calculate the percentage of participants who increased their Behavior Change score, Action scores, or both Behavior Change and Action scores from baseline (i.e., estimated slope > 0) by study arm; p-values adjusted to a significance of 0.017.

1678

1679 For moderator analysis, we will test for interactions by adding interaction terms to the group by 1680 time variable for health literacy (limited versus adequate) controlling for prior ACP 1681 documentation and clustering effects by clinician. All other interaction terms are adjusted for 1682 health literacy (randomization blocking variable) prior ACP documentation and clustering effects 1683 by clinician. Additional interaction terms to be added to the group by time variable include 1684 language (i.e., English versus Spanish), control preferences for decision making (i.e., makes 1685 own decisions versus doctor makes decisions), age (i.e., < 65 years versus \geq 65 years of age), 1686 sex/gender (i.e., self-reported man versus woman), race/ethnicity (i.e., white versus non-white), 1687 health status (i.e., good-to-excellent versus fair-to-poor), presence of a potential surrogate (i.e., 1688 yes versus no), internet access at home (i.e., yes versus no), and, for Spanish-speakers, 1689 patient-clinician language (concordance vs. discordance). A p-value for interaction <0.05 is 1690 considered significant. 1691

Missing data for the primary outcome will be assessed. If there is 10% or more of missing data, we will use a mean imputation approach. All available data will be included in mixed-effects models. We will assess whether any research staff member became unblinded during follow-up assessment and conduct sensitivity analysis as needed.

1696

1697 SAMPLE SIZE AND POWER CALCULATIONS

1698 We will measure a full range of ACP behaviors including discussions. However, written advance 1699 directive completion of legal forms is a primary outcome and is the most well-studied.¹⁰⁰ Power

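### Secondary and exploratory outcomes use single-step Bonferroni, where Holm's step-down test would keep the same 5% family-wise error with somewhat more power at little cost

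*Combined protocol and SAP*

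**What the plan says.** The Statistical Analysis Plan of the final protocol makes all tests two-sided, with the level "set at .05 for the primary outcome and Bonferroni adjusted for secondary" patient-reported outcomes. Those outcomes are the ACP Engagement Survey's Action and Behavior Change measures, the latter described as "Likert scores) from baseline to 1 week, and 3, 6, and 12 months". The section does not count the tests in this family.

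For the post-hoc stakeholder outcome, the same section compares by arm the share of participants with an estimated slope above zero, with "p-values adjusted to a significance of 0.017". There are three such tests. The Summary of Changes to the Protocol (Measures & Data Collection, Sept 20, 2017) describes participants "who improved over time for Behavior Change scores, Actions scores, and both combined" and says that the investigators "used Bonferroni corrections to set the p-value of significance at 0.017".

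The Summary of Changes to the Statistical Analysis Plan records the general rule: "We added Bonferroni adjusted p-values for all secondary and exploratory outcomes". The point does not rest on that log, because the current SAP text says the same. No step-down procedure is mentioned anywhere. A fixed 0.017 for each of three tests is single-step Bonferroni, and that is also the ordinary reading of the unqualified wording for the secondary outcomes.

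**The concern.** Single-step Bonferroni holds every test in a family of m to 0.05/m, whatever the other results are. Holm compares the smallest p-value with 0.05/m, the next with 0.05/(m-1), and so on up to 0.05, stopping at the first failure. Its first step is Bonferroni's, and each later threshold is looser. So it rejects everything Bonferroni rejects and can reject more, and it keeps family-wise error at or below 5% under any dependence between the tests.

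The extra rejections come when more than one effect is real. That is what the secondary hypothesis proposes (Research Aims and Study Hypotheses): PREPARE should raise both behavior change processes and ACP actions. It is also a reasonable planning case, since the Veterans trial summarised under Preliminary Studies reported higher process and action scores at each follow-up. At stake is the chance that one of two genuine effects is called non-significant under a stricter level than 5% error control requires.

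**Working it through.** **The plan's own figures.**
- Exploratory threshold: 0.05/3 = 0.0167, printed as 0.017. It reproduces.
- Scale power (Sample Size and Power Calculations): PREPARE improves by 0.5 SD and controls by 0.1 to 0.2 SD, so the between-arm difference d is 0.4 to 0.3 SD. With non-centrality d x sqrt(n/2), power is approximately Phi(d x sqrt(n/2) - z). At n = 201 per arm and two-sided 0.05 (z = 1.960):
  - d = 0.3: Phi(3.007 - 1.960) = 85.3%
  - d = 0.4: Phi(4.010 - 1.960) = 98.0%

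 The stated 85% to 98% therefore reproduces at the recruited number, before dropout and with no multiplicity correction.

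**Inputs for the comparison.**
- n after the planned 15% dropout: 201 x 0.85 = 170.85, so 171 per arm for one language; 402 x 0.85 = 341.7, so 342 per arm pooled.
- d = 0.3 and 0.4 SD, as above.
- Assumed, because the SAP does not say: a secondary family of two scales (m = 2), equal true effects, correlation 0.3 to 0.7 between the test statistics.

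**Bonferroni per scale.** The level is 0.05/2 = 0.025, so z = 2.241.
- One language, 0.3 SD: 0.3 x sqrt(171/2) = 2.774; Phi(2.774 - 2.241) = 70%. Uncorrected at 0.05 it would be Phi(2.774 - 1.960) = 79%.
- Pooled, 0.3 SD: 0.3 x sqrt(342/2) = 3.923; Phi(3.923 - 2.241) = 95%.

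**Holm against Bonferroni.** Simulation of 400,000 draws of correlated normal test statistics, m = 2:

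| Setting | Power per scale, Bonferroni to Holm | Power for both, Bonferroni to Holm |
|---|---|---|
| 171 per arm, 0.3 SD, correlation 0.3 | 70% to 76% | 53% to 65% |
| 171 per arm, 0.3 SD, correlation 0.7 | 70% to 75% | 59% to 69% |
| 342 per arm, 0.3 SD, correlation 0.5 | 95% to 97% | 92% to 95% |
| 342 per arm, 0.4 SD, correlation 0.5 | gain of 0.2 points or less | gain of 0.2 points or less |

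One language at 0.4 SD gains 2 to 3 points per scale. The chance of at least one rejection is identical under the two methods in every setting.

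**Only one scale real** (171 per arm, 0.3 SD): power for the real effect rises by about 0.2 points or less. False rejection of the null scale rises from 2.5% to about 4.0%, still below 5%. Under the global null the two methods reject in the same draws.

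**Larger secondary family** (175 per arm, the plan's evaluable target; 0.3 SD; correlation 0.5; all effects real). Average power per test rises from 66.0% to 73.7% with m = 3, and from 52.8% to 63.6% with m = 8 (two scales at four visits).

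**Three exploratory tests.** The documents give no effect size for these percentages, so this is illustration only. With a standardised effect of 0.3, 171 per arm and correlation 0.5 to 0.8, power for all three rises from 40-50% to 58-65%.

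**The case against.** The strongest reply is that this is an efficiency preference and not an error. Bonferroni is valid and conservative, the primary outcome is tested at .05 without any adjustment, and one of the two families is openly post-hoc and exploratory. All of that stands. So does the observation that if p-values come out as small as those in the Veterans trial (P <.001), the two procedures agree.

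A reader might infer three stronger things that the documents do not support.

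- *Bonferroni buys nothing.* It gives one printable threshold and simple matching simultaneous confidence intervals, and its actual error is lower when some effects are real (2.5% against about 4.0% for the null scale above). The accurate claim is that Holm costs little.
- *The close relation between the tests makes Holm more valuable here.* The two scales come from one survey, and increasing on both implies increasing on each, so Bonferroni is indeed conservative. But Holm does not use the dependence either. Its gain for showing both scales (171 per arm, 0.3 SD) falls from 11.4 points at correlation 0.3 to 9.6 at 0.7 and 7.8 at 0.9.
- *The families can be left as they are.* The three exploratory tests are defined. The secondary family is not: the SAP lists yes/no actions, a 0-25 scale, Behavior Change scores, four follow-up times, and overall plus by-language analyses, without a count. Holm needs that count as much as Bonferroni does, so changing the method alone would not fix a threshold.

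**Conclusion.** The point holds as a cheap improvement. For the secondary patient-reported outcomes and the three exploratory tests, Holm gives the same 5% family-wise guarantee and never loses a Bonferroni rejection.

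The benefit lies mainly in the by-language analyses, and only if both effects are real and near 0.3 SD, the lower end of the plan's own range: about 5 to 6 points per scale and 10 to 12 points for showing both. In the pooled sample it is about 2 points per scale at 0.3 SD and nothing of consequence at 0.4 SD. These sizes rest on a family of two, equal effects and the assumed correlations; a larger family would gain more. For the exploratory tests only the direction of the gain is established. Nothing here makes the planned analysis invalid or touches the primary conclusion.

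**What to change.** In the final SAP, where it reads "set at .05 for the primary outcome and Bonferroni adjusted for secondary", replace the Bonferroni adjustment with Holm adjustment across a listed secondary family. The list should name each scale, visit and analysis population that counts as a test; the Behavior Change and Action scales are one possible family.

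Where it reads "p-values adjusted to a significance of 0.017", specify Holm across the three tests: smallest p-value against 0.0167, next against 0.025, largest against 0.05, stopping at the first non-significant test. Report ordinary 95% confidence intervals and label them as unadjusted.

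The change should be fixed before arm-level results are seen. The documents do not say whether they have been. If they have, keep Bonferroni as the planned result and show Holm beside it.

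The cost is two SAP sentences and the list, with no new data, participants or models. What is given up is a single printed threshold, simple simultaneous intervals, and some of Bonferroni's slack below 5%.
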